The Pittsburgh Sleep Quality Index (PSQI): a self-rated questionnaire which assesses sleep quality and disturbances over a 1-month time interval. In scoring the PSQI, there are seven component scores with each scored 0 (no difficulty) to 3 (severe difficulty). The component scores are summed to produce total score (range 0 to 21). Higher scores indicate worse sleep quality.

World Health Organization Quality of Life (WHOQOL) questionnaire - Brief, Taiwan version: a questionnaire including 28 items with each score 0-4. Higher score indicate better quality of life.

Edinburgh Postnatal Depression Scale: a set of 10 screening questions with each score 0 to 3 that can indicate whether a parent has symptoms that are common in women with depression and anxiety during pregnancy and in the year following the birth of a child. Higher score indicate higher risk of postnatal depression.

[Time Frame: at their child birth]

2. Maternal quality of life

Maternal quality of life assessed by

The Pittsburgh Sleep Quality Index (PSQI): a self-rated questionnaire which assesses sleep quality and disturbances over a 1-month time interval. In scoring the PSQI, there are seven component scores with each scored 0 (no difficulty) to 3 (severe difficulty). The component scores are summed to produce total score (range 0 to 21). Higher scores indicate worse sleep quality.

World Health Organization Quality of Life (WHOQOL) questionnaire - Brief, Taiwan version: a questionnaire including 28 items with each score 0-4. Higher score indicate better quality of life.

Edinburgh Postnatal Depression Scale: a set of 10 screening questions with each score 0 to 3 that can indicate whether a parent has symptoms that are common in women with depression and anxiety during pregnancy and in the year following the birth of a child. Higher score indicate higher risk of postnatal depression.

[Time Frame: at their child 1-month-old]

3. Maternal quality of life

Maternal quality of life assessed by

The Pittsburgh Sleep Quality Index (PSQI): a self-rated questionnaire which assesses sleep quality and disturbances over a 1-month time interval. In scoring the PSQI, there are seven component scores with each scored 0 (no difficulty) to 3 (severe difficulty). The component scores are summed to produce total score (range 0 to 21). Higher scores indicate worse sleep quality.

World Health Organization Quality of Life (WHOQOL) questionnaire - Brief, Taiwan version: a questionnaire including 28 items with each score 0-4. Higher score indicate better quality of life.

Edinburgh Postnatal Depression Scale: a set of 10 screening questions with each score 0 to 3 that can indicate whether a parent has symptoms that are common in women with depression and anxiety during pregnancy and in the year following the birth of a child. Higher score indicate higher risk of postnatal depression.

[Time Frame: at their child 3-month-old]

4. Maternal quality of life

Maternal quality of life assessed by

The Pittsburgh Sleep Quality Index (PSQI): a self-rated questionnaire which assesses sleep quality and disturbances over a 1-month time interval. In scoring the PSQI, there are seven component scores with each scored 0 (no difficulty) to 3 (severe difficulty). The component scores are summed to produce total score (range 0 to 21). Higher scores indicate worse sleep quality.

World Health Organization Quality of Life (WHOQOL) questionnaire - Brief, Taiwan version: a questionnaire including 28 items with each score 0-4. Higher score indicate better quality of life.

Edinburgh Postnatal Depression Scale: a set of 10 screening questions with each score 0 to 3 that can indicate whether a parent has symptoms that are common in women with depression and anxiety during pregnancy and in the year following the birth of a child. Higher score indicate higher risk of postnatal depression.

[Time Frame: at their child 6-month-old]

Secondary Outcome Measures:

Neonate and infant' health condition

Neonate and infant' health conditions including functional gastrointestinal disorders, diaper dermatitis, and atopic dermatitis.

Functional Gastrointestinal Disorders in Infancy including infantile colic and regurgitation: use questionnaires according to ROME-IV criteria, and higher score indicate worse condition of functional gastrointestinal disorders in infancy.

Diaper dermatitis: use a self-rated questionnaire to determine the condition of diaper dermatitis

Atopic dermatitis: use a self-rated questionnaire to determine the condition of atopic dermatitis

[Time Frame: at baby's 1-month-old]

Neonate and infant' health condition

Neonate and infant' health conditions including functional gastrointestinal disorders, diaper dermatitis, and atopic dermatitis.

Functional Gastrointestinal Disorders in Infancy including infantile colic and regurgitation: use questionnaires according to ROME-IV criteria, and higher score indicate worse condition of functional gastrointestinal disorders in infancy.

Diaper dermatitis: use a self-rated questionnaire to determine the condition of diaper dermatitis

Atopic dermatitis: use a self-rated questionnaire to determine the condition of atopic dermatitis

[Time Frame: at baby's 3-month-old]

Neonate and infant' health condition

Neonate and infant' health conditions including functional gastrointestinal disorders, diaper dermatitis, and atopic dermatitis.

Functional Gastrointestinal Disorders in Infancy including infantile colic and regurgitation: use questionnaires according to ROME-IV criteria, and higher score indicate worse condition of functional gastrointestinal disorders in infancy.

Diaper dermatitis: use a self-rated questionnaire to determine the condition of diaper dermatitis

Atopic dermatitis: use a self-rated questionnaire to determine the condition of atopic dermatitis

[Time Frame: at baby's 6-month-old]

Eligibility

Baby's Age: 1-day-old to 7-day-old

Mother's Age: 20 to 50-year-old

Baby's Sex: All

Criteria:

<Participants of neonates>

Inclusion Criteria :

- Gestational age more than 37 to less than 41 weeks
- Age less than 1 week on entry into the study
- Birth weight adequate for gestational age
- Apgar score of more than 8 at 10 minutes

Exclusion Criteria:

- Congenital disorders and/or clinical or physical alterations at clinical examination
- Antibiotic or probiotic administration before inclusion
- Admission to ICU

<Participants of neonates' mother>

Inclusion Criteria:

- (1) Aged between 20-50 and baby included in our study

Exclusion Criteria:

- (1) Diagnosed as psychiatric disease during antepartum period or before pregnancy

Study protocol

Infant participants who meet the inclusion criteria will be included, and they will be categorized randomly into experimental group or placebo group. Experimental group will be given experimental agent including vitamin D3 and probiotics for total 90 days. Placebo group will be given placebo agent including vitamin D3 for total 90 days. We will also record infant's birth record at the same time. For both groups, we will ask infant participant's mother about baby's health condition and maternal quality of life by using PSQI, WHOQOL, and Edinburgh Postnatal Depression Scale at the timing of their baby's birth, at baby's 1-month-old, baby's 3-month-old, and baby's 6-month-old.

Statistical analysis

Demographic data, maternal life quality, and infant's health condition will be presented as mean \pm standard deviation, median , or percentile. Independent-Sample t test and hi-square test was performed to evaluate the associations between probiotics use and maternal lift quality and infant's health condition. Statistical significance was defined as p value <0.05 . All statistical analyses were performed with Statistical Analysis System, Statistical Package for the Social Sciences or Statistics with R .

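### Maternal scores at birth are listed as a primary outcome instead of as the baseline, so 3 of the 12 listed instrument-by-visit primary measures, read literally, cannot show a probiotic effect

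*Protocol*

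**What the plan says.** Under Outcome measures, the protocol lists four numbered primary entries, all named maternal quality of life and all made up of the same three instruments: PSQI, WHOQOL-Brief (Taiwan version) and the Edinburgh Postnatal Depression Scale. They differ only in timing. Entry 1 reads "Time Frame: at their child birth", entry 2 "Time Frame: at their child 1-month-old", entry 3 "Time Frame: at their child 3-month-old", and entry 4 is at six months. The PSQI is described as "a self-rated questionnaire which assesses sleep quality and disturbances over a 1-month time interval".

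Eligibility sets the infant's age at entry: "Baby's Age: 1-day-old to 7-day-old". The Study protocol section puts inclusion before allocation ("Infant participants who meet the inclusion criteria will be included, and they will be categorized randomly into experimental group or placebo group"), and the agent is then given for 90 days. The same section has the mothers questioned "at the timing of their baby's birth, at baby's 1-month-old, baby's 3-month-old, and baby's 6-month-old".

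The only comparative analysis named, under Statistical analysis, is a t test and a chi-square test that "was performed to evaluate the associations between probiotics use and maternal lift quality and infant's health condition", with significance at p below 0.05. The birth score is given no role as baseline, covariate or reference for change.

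**The concern.** An outcome has to be something the intervention can alter. A score taken at the infant's birth comes before inclusion, before allocation and before the first administration. The PSQI completed then looks back over the last month of pregnancy. Under sound randomization, a difference between the arms on such a score can only be chance, yet the listing would allow it to be reported as a primary result.

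The word birth may instead stand for the first contact at enrolment, some time in the first week. The difficulty then takes another form. Nothing fixes whether the mother completes the questionnaires before she enters the allocation and dosing steps with her infant, so the score is not guaranteed to be a pre-treatment measurement. On either reading, a measurement that is already being collected and is well suited to be the baseline is classed as an outcome.

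**Working it through.** **Order of events.** Set side by side, the sections give: birth; entry at 1 to 7 days old (Eligibility); inclusion and then randomization (Study protocol); agent for 90 days. Read literally, entry 1 falls before all the later steps. If the questionnaire is instead completed as late as day 7, at most about 7/30 = 23% of the PSQI recall period falls after birth, so even then the score mostly describes pregnancy.

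**Contrast within the protocol.** The secondary infant outcomes begin at 1 month and have no birth time point.

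**Count.** Taking one score per instrument, as the outcomes are listed:

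- all primary cells: 3 instruments × 4 visits = 12
- cells at birth: 3 × 1 = 3, and 3/12 = 25%
- cells left after birth is removed: 12 − 3 = 9

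The protocol gives no figure of its own on this point. Its sample size of 110 per arm states no effect size, and the argument does not depend on it.

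**False positives at birth, if each score is tested at 0.05.** For independent tests, 1 − 0.95³ = 0.143. The three scales are probably correlated, but the protocol gives no correlation. A simulation of three two-sided t tests with no true difference and 110 per arm (40,000 trials, Monte Carlo standard error about 0.002) gave:

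| Assumed correlation between scales | Chance of at least one p < 0.05 |
|---|---|
| 0.3 | 0.138 |
| 0.5 | 0.127 |
| 0.7 | 0.112 |

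**What the same score could do as a covariate.** Let ρ be the correlation between the birth score and a later score. The protocol does not give it, so a range is assumed. Adjustment multiplies the residual variance by 1 − ρ² and the confidence interval width by √(1 − ρ²). With the stated 10% dropout, 110 × 0.9 = 99 per arm remain, and the unadjusted sample of equal precision is 99/(1 − ρ²).

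| Assumed ρ | Variance factor | Interval width factor | Equivalent unadjusted n per arm |
|---|---|---|---|
| 0.3 | 0.91 | 0.954 | 109 |
| 0.4 | 0.84 | 0.917 | 118 |
| 0.5 | 0.75 | 0.866 | 132 |
| 0.6 | 0.64 | 0.800 | 155 |

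Residual variance therefore falls by 9–36% and interval width by 5–20%.

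**The case against.** The strongest reply is that this is only a label. A mother qualifies only through an enrolled infant, and infants enter from day 1, so no enrolled mother can be assessed literally at birth. The workable reading is the enrolment contact, and most readers would take it as a baseline. The protocol lists outcomes, not tests: it does not say that each instrument is tested at each visit or that birth is tested separately. Baseline adjustment is ordinary SAP content, and an unadjusted comparison of the later scores is valid in a randomized trial. A difference known to precede treatment would hardly be believed as a probiotic effect, and it might point to an allocation fault rather than chance. Removing the birth cells lowers the family-wise error, if all tests were independent, only from 0.46 (12 tests) to 0.37 (9 tests).

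Several of these points stand. The 3 in 12 counts listed cells, not declared tests, and scoring the WHOQOL by domain would change the count. The 11–14% applies only if the birth scores are tested. The covariate gains rest on assumed correlations and measure a missed benefit, not bias. The later comparisons remain valid, and multiplicity among the other nine is a separate matter.

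The main point survives. The document gives the birth score numbered primary status, and its one description of comparative testing makes no exception for it. Reading birth as enrolment does not help, because the order of questionnaire, randomization and first administration is then open. A SAP could add a covariate, but that would not correct the protocol's own list of primary outcomes.

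**Conclusion.** The concern holds. Three of the 12 listed instrument-by-visit primary measures (25%) are taken before treatment on the literal reading, or at an unfixed point around its start on the looser one, and are wrongly classed as outcomes. The count assumes one score per instrument. If the three are tested at 0.05, they carry an 11–14% chance of at least one spurious primary finding, the range depending on the assumed correlation between scales. Used as covariates at an assumed ρ of 0.3–0.6, the same scores would narrow intervals by 5–20%. The trial is not invalidated, since the 1-, 3- and 6-month scores remain sound outcomes. The correction should be made because it mends the primary outcome list at almost no cost.

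**What to change.** Take the birth time point out of the primary outcomes and define it as the baseline score, completed at enrolment before randomization and before the first administration. Present it descriptively by arm without a significance test, and use it as the covariate when the later scores are compared. Keep only the 1-, 3- and 6-month scores as outcomes.

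The cost is a change of wording in the protocol and the registry entry, and a fixed sequence at enrolment: questionnaires, then randomization, then first administration. No visit, questionnaire or participant is added.
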